## 8.2. Reporting Period

Serious adverse events require immediate notification to sponsor or its designated representative beginning from the time that the patient provides informed consent, which is obtained prior to the patient's participation in the clinical trial, ie, prior to undergoing any trial-related procedure and/or receiving investigational product, through and including 28 calendar days after the last administration of the investigational product. Any serious adverse event occurring any time after the reporting period must be promptly reported if a causal relationship to investigational product is suspected.

Non-serious adverse events should be recorded from the time the patient has taken at least one dose of trial treatment through last patient visit.

If a patient begins a new anticancer therapy, the adverse event reporting period for non-serious adverse events ends at the time the new treatment is started. Death must be reported if it occurs during the serious adverse event reporting period after the last dose of investigational product, irrespective of any intervening treatment.

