#### 8.5. Serious Adverse Events

A serious adverse event or serious adverse drug reaction is any untoward medical occurrence at any dose that:

- Results in death;
- Is life-threatening (immediate risk of death);
- Requires inpatient hospitalization or prolongation of existing hospitalization;
- Results in persistent or significant disability/incapacity;

• Results in congenital anomaly/birth defect.

Progression of the malignancy under trial (including signs and symptoms of progression) should not be reported as a serious adverse event unless the outcome is fatal during the trial or within the safety reporting period. Hospitalization due to signs and symptoms of disease progression should not be reported as serious adverse event. If the malignancy has a fatal outcome within the safety reporting period, then the event leading to death must be recorded as an adverse event and as a serious adverse event with CTCAE Grade 5 (See Section 8.7, Severity Assessment). Any histopathologically confirmed secondary malignancy must be reported as SAE.

Medical and scientific judgment should be exercised in determining whether an event is an important medical event. An important medical event may not be immediately life-threatening and/or result in death or hospitalization. However, if it is determined that the event may jeopardize the patient and/or may require intervention to prevent one of the other outcomes listed in the definition above, the important medical event should be reported as serious.

Examples of such events are intensive treatment in an emergency room or at home for allergic bronchospasm; blood dyscrasias or convulsions that do not result in hospitalization; or development of drug dependency or drug abuse.

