**3.2.3. Blinding**

The study is double-blind. Axitinib will be supplied as 1 mg and 5 mg film-coated tablets for oral administration in light-protecting bottles. Placebo will match all dose formulations and will be identical in appearance to the active study drug.

At the initiation of the trial, the trial site will be instructed on the method for breaking the blind. The method will be an electronic process. Blinding codes should only be broken in emergency situations for reasons of subject safety, or if the subject has a confirmed recurrence or occurrence of a secondary malignancy with limited alternative treatment option and knowledge of study drug is required to facilitate further treatment decisions. For those with suspected recurrence, the site must await results from the IRC. The decision to break the blind must be approved by the Sponsor prior to doing so. When the blinding code is broken, the reason must be fully documented in the site source document. In these instances, only the principal investigator (PI) is unblinded. The broader study team will remain blinded.

Where unblinded study data is to be produced for review by the DMC for the study, a biostatistics team in a separate location from the study team will be used to produce and distribute the unblinded data. The data will only be distributed to unblinded personnel as agreed in a separate DMC analysis plan and/or DMC charter.

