**7.5.1. Adverse Events**

Adverse event (AE) terms recorded on the CRF will be mapped to PT and SOC using the Medical Dictionary for Regulatory Activities (MedDRA). The severity of AEs will be evaluated by the investigator by employing the CTCAE v4.03 (Cancer Terminology Criteria for Adverse Events). The investigator will also judge each event to be “not related” or “related” to study treatment.

A TEAE is defined as any AE with an onset date on or after the date of the first dose of study treatment or any ongoing event on the date of the first dose of study treatment that worsens in severity after the date of the first dose of study treatment.

The AE observation period is defined as the time from date of the first dose of study treatment until 28 days after the last dose of study drug is administered. TEAEs with an onset date through the end of the study observation period will be summarized by treatment arms. The Grade 5 TEAEs with onset date outside of the observation period may be tabulated separately.

For summaries of subject incidence of TEAE, at each level of summarization, a subject will be counted only once for each AE preferred term experienced by the subject within that level (i.e., multiple episodes of events with the same preferred terms will be counted only once). Selected summaries of subject-incidence of AEs (as defined in Section 7.5.1.2) will include the risk difference (defined as the proportion with the event in the axitinib arm minus the proportion with the event in the placebo treatment arm) with 95% CIs and the risk ratio (or relative risk; defined as the proportion with the event in the axitinib group divided by the proportion with the event in the placebo group) with 95% CIs. An overall summary of treatment emergent adverse events (including those that stopped more than 28 days after the decision to discontinue study treatment) will be provided with the number and percent of subjects who experienced the following in each treatment group:

- Subjects with a TEAE
- Subjects with a Related TEAE
- Subjects with a Serious TEAE at any time (including active treatment period plus follow-up period)
- Subjects with a Serious Related TEAE
- Subjects with a Worst-Grade of  $\geq 3$  TEAE
- Subjects with a Worst-Grade of  $\geq 3$  Related TEAE
- Subjects with a Grade 5 TEAE at any time

---

|           |   |                 |           |
|-----------|---|-----------------|-----------|

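### The serious-TEAE row in SAP 7.5.1 extends into follow-up, where SAEs are collected selectively, so its per-arm percentage mixes complete and incomplete data

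*SAP*

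**What the plan says.** **Collection.** Protocol 8.2 requires SAEs, whatever their cause, from informed consent "through and including 28 calendar days after the last administration of the investigational product". Beyond that point the rule changes: "Any serious adverse event occurring any time after the reporting period must be promptly reported if a causal relationship to investigational product is suspected". Protocol 8.5 has two provisions that may reach further. One has no stated time limit or causality condition: "Any histopathologically confirmed secondary malignancy must be reported as SAE". The other makes fatal progression reportable if it occurs during the trial or within the safety reporting period, which may extend past day 28.

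**Analysis.** SAP 7.5.1 defines treatment emergence with no end date: "A TEAE is defined as any AE with an onset date on or after the date of the first dose of study treatment", plus worsening of events already ongoing. It then sets an observation period that runs "until 28 days after the last dose of study drug is administered" and states: "TEAEs with an onset date through the end of the study observation period will be summarized by treatment arms". The overall summary that follows nevertheless lists "Subjects with a Serious TEAE at any time (including active treatment period plus follow-up period", as a number and percent in each arm. For Grade 5 events the same list has both an any-time row and a row limited to 28 days after the last dose. For serious TEAEs of any cause it has only the any-time row. Protocol 9.4.1 stops treatment emergence at 28 days after treatment.

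**The concern.** A percentage of subjects with a serious event is interpretable if all such events in a stated window are sought in everyone. This row spans two collection regimes. Up to day 28 after the last dose it counts everything. Afterwards it counts mainly what an investigator judged possibly drug-related. The result is neither an on-treatment SAE risk nor a whole-study SAE risk.

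Two things are at stake. First, the row is labelled as covering any time but omits most unrelated late SAEs, so it understates any-time risk in both arms. Second, the arms can differ for reasons other than true risk. Attribution may differ if characteristic drug effects suggest the assignment, or if the code has been broken to the investigator after a confirmed recurrence (SAP 3.2.3: "only the principal investigator (PI) is unblinded"). Time off treatment may also differ: the arm that stops earlier spends more of the study under the narrower reporting rule.

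**Working it through.** **Step 1: which events can enter the row.**

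| Onset | SAEs required by the protocol | Counted in the SAP row |
|---|---|---|
| First dose to 28 days after last dose | All causes (8.2) | Yes |
| Later | Suspected related (8.2); confirmed secondary malignancy and possibly fatal progression (8.5) | Yes, where collected |

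The second line is where collection narrows and the row does not.

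**Step 2: does follow-up here mean beyond day 28?** The Grade 5 rows say so. Listing an any-time row beside a 28-day row makes sense only if the first reaches further. SAP 7.5.5, on anti-tumor drugs, also treats follow-up as starting more than 28 days after the last day of treatment.

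**Step 3: how long is the selective period?** SAP 3.1 estimates 5 years (60 months) from first subject to final analysis, and treatment lasts at most 3 years (36 months). A patient enrolled at the start who completes treatment has about 60 - 36 = 24 months after stopping. One who stops at 12 months has about 60 - 12 = 48.

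**Step 4: illustrative size.** The plan states no figure to reproduce, and the documents give no SAE rates. Every rate below is an assumption, with true risks set equal in both arms:

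- p0 = risk of an SAE to 28 days after last dose: 10% or 20%
- q = risk of an SAE later, taken as independent of p0: 15%
- c = share of late SAEs reported: 5% on placebo, 5% to 40% on axitinib

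A subject counts once, so a late SAE adds to the row only if there was none earlier:

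row = 1 - (1 - p0)(1 - q·c)

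difference = (1 - p0)·q·(c_axitinib - c_placebo)

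| | p0 = 10% | p0 = 20% |
|---|---|---|
| Placebo row, c = 5% | 1 - 0.90 × 0.9925 = 10.7% | 1 - 0.80 × 0.9925 = 20.6% |
| Axitinib row, c = 40% | 1 - 0.90 × 0.94 = 15.4% | 1 - 0.80 × 0.94 = 24.8% |
| Spurious difference | 0.90 × 0.15 × 0.35 = 4.7 points | 0.80 × 0.15 × 0.35 = 4.2 points |
| True any-time risk, both arms | 1 - 0.90 × 0.85 = 23.5% | 1 - 0.80 × 0.85 = 32.0% |

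With c = 5% in both arms the difference is 0, but each arm shows 10.7% against a true 23.5%, or 20.6% against 32.0%.

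**Step 5: sensitivity.** Letting q run from 5% to 20%, reporting of 40% against 5% gives 1.4 to 6.3 points. Reporting of 20% against 10% gives 0.4 to 1.8 points.

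**Step 6: after the change.** A row limited to 28 days equals p0 in both arms under these assumptions, whatever the value of c.

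**The case against.** Several stronger readings are tempting, and the documents do not support them.

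- *A planned arm comparison is biased.* SAP 7.5 plans no formal safety comparison. SAP 7.5.1 ties risk differences and risk ratios to the selected summaries of 7.5.1.2 (events of special interest). This row is a count and percent, so any comparison is one a reader makes by eye.
- *Late SAEs are collected only if suspected drug-related.* Protocol 8.5 provides for confirmed secondary malignancies and perhaps fatal progression. Footnote 18 of the Schedule of Assessments also extends adverse event collection while serious or drug-related toxicities remain unresolved. These exceptions make late capture vary by event type and patient. They do not make it complete.
- *Fatal events are obscured too.* Grade 5 TEAEs have a 28-day row, and SAP 7.5.1.1 splits all reported deaths at 28 days.
- *The SAP provides no 28-day SAE display at all.* Only the listed summary can be checked. The table shells are not in the text available, and the general observation-period sentence could yield such a table.
- *Unblinding distorts attribution.* The trial is double-blind. Breaking the code after recurrence needs confirmed recurrence or secondary malignancy, limited alternatives, a need to know for further treatment, and sponsor approval (Protocol 5.2, SAP 3.2.3). The documents give no frequency and no evidence that attribution differs by arm.

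It can also be argued that follow-up means only the 28-day visit of Protocol 6.3. The paired Grade 5 rows and SAP 7.5.5 weigh against that. If it were the intent, the label would still need correcting. Finally, in the illustration the distortion adds events to axitinib, so it would not hide harm relative to placebo. That is fair, but the direction rests on the assumed reporting shares.

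What stands is that one all-cause row pools two collection regimes and contradicts the 28-day limits stated elsewhere.

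**Conclusion.** The point holds as a defect in one descriptive safety row. The row's window runs past the end of all-cause SAE collection. It conflicts with the SAP's own observation period and with the protocol's definition of treatment emergence. The listed summary has no 28-day all-cause serious row to read in its place.

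The consequence is a percentage that understates any-time SAE risk and could differ between arms if attribution or time off treatment differs. Under the assumed rates (equal true risk of 10-20% to day 28 and 15% later; late reporting of 5% on placebo and 5-40% on axitinib) the artefact is between 0 and about 4.2-4.7 percentage points. The top of that range requires an eight-fold difference in reporting, for which the documents give no evidence. The understatement needs only that some late SAEs are unrelated and unreported. No efficacy analysis, error rate or stopping boundary is affected.

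**What to change.** In SAP 7.5.1 and the matching table shell, define the main row as subjects with a serious TEAE whose onset lies between first dose and 28 days after last dose, all causes. Put serious events with later onset in a separate row or listing, labelled as selectively collected: suspected related, confirmed secondary malignancy, and fatal progression if it is collected at that stage. Keep the 28-day Grade 5 row and the death table in 7.5.1.1 unchanged. State the 28-day limit in the SAP's definition of a TEAE so that it agrees with Protocol 9.4.1.

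The cost is wording in the SAP and shells. No new data are needed and no event is lost, although the main SAE count becomes slightly smaller. The revised row will not equalise exposure if one arm stops treatment earlier, but its window will be one in which all SAEs were required to be reported.

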**Statistical Analysis Plan**

- Subjects with a Grade 5 TEAE through 28 days of last dose of the study treatment
- Subjects with a Related Grade 5 TEAE at any time
- Subjects with a TEAE leading to dose modification (dose reduction or temporary interruption/discontinuation)
- Subjects with a TEAE leading to dose reduction
- Subjects with a TEAE leading to temporary dose interruption/discontinuation
- Subjects with TEAE leading to permanent discontinuation

**7.5.1.1 Deaths**

All reported subject deaths and whether death was causally associated with the disease under study will be summarized by treatment arm in the as-treated population.

Deaths will be summarized in 2 main categories as follows:

- Deaths within 28 days after the date of receipt of the last dose of study treatment
- Deaths greater than 28 days after the date of receipt of last dose of study treatment

Summary of primary cause of death will be tabulated causality to study disease and relationship to study drug.

**7.5.1.2 Treatment Emergent Adverse Events of Special Interest**

The following TEAEs of special interests will be summarized for the as-treated population and by SOC and PT for each categorized treatment group. The list of MedDRA defined SOC and PTs for TEAEs of special interest are provided below and may be updated at the time of database lock based on the MedDRA version in use at the time of reporting and/or any additional safety information available from the Axitinib program that may determine a need to consider additional events of interest. Additionally, for the following special adverse events, Kaplan-Meier methods will be used to display the time to the first occurrence of each of these 13 event categories, if the number of events is  $\geq 10$  events per treatment arm:

| Adverse Events of Special Interest | Search Terms (MedDRA version 20.1)  |
|---|--|
| Cardiac disorders                         | Cardiac disorders – SOC
Cardiac and vascular investigations (excluding enzyme tests)- HLGT  |
| Nervous system disorders                  | Central nervous system vascular disorders- HLGT  |
| Vascular disorders                        | Embolism and thrombosis- HLGT
Pulmonary Embolism PT   |
| Renal vascular disorders                  | Renal vascular and ischaemic conditions (HLT)
Renal failure and impairment (HLT)
Renal hypertension and related conditions (HLT) |

Document: C:\Users\q764206\AppData\Local\Microsoft\Windows\Temporary Internet Files\Content.Outlook\GWW33WM3\ATLAS\_SAPFinal v8.0\_06MAR2018.docx  
 Author: [name] (Updated [name]; [name]; [name], [name]) Version Number: Final 8.0

Version Date: 06MAR2018

Template No: CS\_TP\_BS016 – Revision 2 Reference: CS\_WI\_BS005  
 Effective Date: 01Feb2010

Statistical Analysis Plan

|   |   |
|---|---|
| Haemorrhage                                 | Haemorrhage (excluding lab terms) SMQ (broad and narrow) and Haemorrhage laboratory terms SMQ (broad and narrow)  |
| Hypertension                                | Hypertension SMQ narrow   |
| Proteinuria                                 | MedDRA PTs: Albumin urine present, Proteinuria, Protein urine, and Protein urine present  |
| Thyroid Dysfunction                         | Thyroid dysfunction SMQ broad   |
| Venous Embolic and Thrombotic Events (VTE)  | Embolic and thrombotic events, venous SMQ narrow  |
| Palmar-Plantar Erythrodysesthesia (PPE)     | MedDRA PTs: Palmar-plantar erythrodysesthesia syndrome, palmar erythema, and plantar erythema.  |
| Fatigue and Asthenic Conditions             | MedDRA PTs: Asthenia, Autonomic nervous system imbalance, Decreased activity, Listless, Sluggishness, Chronic fatigue syndrome, Fatigue and Malaise)  |
| Hepatic Disorders                           | Cholestasis and jaundice of hepatic origin (SMQ narrow)
Drug-related hepatic disorders - comprehensive search (SMQ narrow)
Liver related investigations, signs and symptoms (SMQ narrow)
Hepatic & Hepatobiliary disorders (HLGT)  |
| Congestive Heart Failure/Cardiomyopathy     | MedDRA PTs: Acute left ventricular failure, Acute right ventricular failure, Cardiac failure, Cardiac failure acute, Cardiac failure chronic, Cardiac failure congestive, Cardiac failure high output, Cardiogenic shock, Cardiopulmonary failure, Chronic left ventricular failure, Chronic right ventricular failure, Cor pulmonale, Cor pulmonale acute, Cor pulmonale chronic, Ejection fraction decreased, Left ventricular failure, Low cardiac output syndrome, Neonatal cardiac failure, Right ventricular failure, Ventricular failure, Cardiac output decreased, Cardio-respiratory distress, Central venous pressure increased, Diastolic dysfunction, Left ventricular dysfunction, Myocardial depression, Oedema due to cardiac disease, Right ventricular dysfunction, Systolic dysfunction, Ventricular dysfunction, Cardiomyopathy acute, Congestive cardiomyopathy, Ejection fraction abnormal, Ejection fraction decreased. |
| Carcinogenicity (Second Primary Malignancy) | SMQ malignant or unspecified tumours, SMQ Malignant tumours, SMQ Tumours of unspecified malignancy and the Lower Level Term (LLT): Secondary primary malignancy.  |

For Cardiovascular disorders: Include Cardiac disorders, Nervous system disorders, Vascular disorders

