In the subgroup of 251 patients who received prior treatment with cytokines (126 in the axitinib arm and 125 in the sorafenib arm), the median PFS in the axitinib arm was 12.1 months (95% CI [10.1, 13.9]) compared with 6.5 months (95% CI [6.3, 8.3]) in the sorafenib arm, with a hazard ratio of 0.464 (95% CI [0.318, 0.676]) and a p-value of <0.0001 (1-sided). The sorafenib control arm replicated prior Phase 3 sorafenib data (median PFS of 5.5 months) in a cytokine-refractory population. In the subgroup of 389 patients who had received prior treatment with sunitinib-containing regimen (194 in the axitinib arm and 195 in the sorafenib arm), the median PFS in the axitinib arm was 4.8 months (95% CI [4.5, 6.4]) compared with 3.4 months (95% CI [2.8, 4.7]) in the sorafenib arm, with a hazard ratio of 0.741 (95% CI [0.573, 0.958]) and a p-value of 0.0107 (1-sided). The study enrolled only 59 patients who received prior treatment with bevacizumab-containing regimen (29 in the axitinib arm and 30 in the sorafenib arm) and 24 patients who received prior treatment with temsirolimus-containing regimen (12 in the axitinib arm and 12 in the sorafenib arm). Due to small numbers of patients in these subgroups, no firm conclusions can be made.

[figure not shown]

Figure 2 Kaplan-Meier Curve for Progression-Free Survival by Independent Assessment for the Overall Population

Since only a total of 223 patients (approximately 30%) had died as of the data cutoff date (31 August 2010), the data for OS are not mature and likely to change with further followup. As of the data cutoff date, the median OS was not reached in the axitinib arm and was 18.9 months in the sorafenib arm, with a hazard ratio of 1.008 with a 95% CI of (0.774, 1.313) and a 1-sided p-value of 0.525. Further follow-up of OS is continuing.

Table 1 presents adverse reactions reported in patients who received axitinib or sorafenib:

**Table 1** Adverse Reaction (Phase III study)

	Axi	tinib	Sorafenib		
	N=	359	N=355		
Adverse Reaction a	All Grades	Grade 3/4	All Grades	Grade 3/4	
	%	%	%	%	
Diarrhea	55	11	53	7	
Hypertension	40	16	29	11	
Fatigue	39	11	32	5	
Decreased appetite	34	5	29	4	
Nausea	32	3	22	1	
Dysphonia	31	0	14	0	
Palmar-plantar erythrodysesthesia syndrome	27	5	51	16	
Weight decreased	25	2	21	1	
Vomiting	24	3	17	1	
Asthenia	21	5	14	3	
Constipation	20	1	20	1	
Hypothyroidism	19	<1	8	0	
Cough	15	1	17	1	
Mucosal inflammation	15	1	12	1	
Arthralgia	15	2	11	1	
Stomatitis	15	1	12	<1	

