### 3. Study Design

#### 3.1. General Description

This is a prospective, randomized, double-blind placebo controlled Phase 3 trial of oral axitinib starting at 5 mg twice daily vs. placebo given for up to 3 years, with a minimum of 1 year, in subjects at high risk of recurrent RCC aged 18 or over (20 or over in Japan, Korea and Taiwan). The dose may be increased or decreased depending on individual subject tolerance of axitinib.

Approximately 700 subjects will be randomized in a 1:1 ratio between axitinib vs placebo. Subjects should begin study treatment within 7 days after randomization. Randomization will occur no sooner than 4 weeks post nephrectomy and no later than 12 weeks post nephrectomy.

Recurrence or occurrence of a secondary malignancy will be followed up at clinic visits until the time of the final analysis (regardless of the duration of treatment) every 16 weeks for the first 3 years from initiation of study treatment (also, at the end of treatment) and every 6 months

---

|           |   |                 |           |
|-----------|---|-----------------|-----------|
| Document: | C:\Users\q764206\AppData\Local\Microsoft\Windows\Temporary Internet Files\Content.Outlook\GWW33WM3\ATLAS_SAPFinal v8.0_06MAR2018.docx |                 |           |
| Author:   | [name] (Updated [name]; [name]; [name], [name])  | Version Number: | Final 8.0 |
|           |   | Version Date:   | 06MAR2018 |

Template No: CS\_TP\_BS016 – Revision 2  
Effective Date: 01Feb2010

Reference: CS\_WI\_BS005

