**7.5. Analysis of Safety**

All safety analyses will be performed using the As-Treated population. No formal comparisons between the two treatment arms are planned. Safety and tolerability will be assessed by the incidence of treatment emergent-adverse events (TEAEs), changes in laboratory parameters and vital signs from baseline, and ECG.

An independent DMC will monitor safety during the study on a regular basis. The committee will operate independently from the Sponsor and the clinical investigators.

The primary responsibility of the DMC is to review the accumulating safety data on a regular and an ad hoc basis and make recommendations to the Sponsor regarding the continued conduct of the study. Safety data will be provided at regular intervals to the DMC in the form of summary reports or data listings from the Sponsor or its designated representative.

Details regarding DMC membership, schedule and format of meetings, format for presentation of data, access to interim data, method and timing of providing interim reports to the DMC, and

---

|           |   |                 |           |
|-----------|---|-----------------|-----------|
| Document: | C:\Users\q764206\AppData\Local\Microsoft\Windows\Temporary Internet Files\Content.Outlook\GWW33WM3\ATLAS_SAPFinal v8.0_06MAR2018.docx |                 |           |
| Author:   | [name] (Updated [name]; [name]; [name], [name])  | Version Number: | Final 8.0 |
|           |   | Version Date:   |           |

06MAR2018

Template No: CS\_TP\_BS016 – Revision 2  
 Effective Date: 01Feb2010

Reference: CS\_WI\_BS005

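### Requiring at least 10 events in each arm may hide the time-to-onset curves for adverse events of special interest that are rare on placebo

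*SAP*

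**What the plan says.** SAP 7.5.1.2 lists the categories of adverse events of special interest. All of them are tabulated without any minimum count: "The following TEAEs of special interests will be summarized for the as-treated population and by SOC and PT". A figure is then added for time to onset: "Kaplan-Meier methods will be used to display the time to the first occurrence of each of these 13 event categories". The same sentence makes this conditional on a count of at least 10 "events per treatment arm". No pooled or either-arm alternative is offered, and no reason is given for the cut-off.

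Two neighbouring statements limit how much depends on this. SAP 7.5.1 says "Selected summaries of subject-incidence of AEs (as defined in Section 7.5.1.2) will include the risk difference", together with the risk ratio, both with 95% confidence intervals. SAP 7.5 makes the safety analysis descriptive: "No formal comparisons between the two treatment arms are planned".

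**The concern.** A toxicity caused by the drug tends to be frequent on axitinib and uncommon on placebo. A rule that both arms must reach 10 can then fail because of the placebo arm alone, however many axitinib subjects are affected. For a fixed axitinib rate, the greater the contrast between arms, the fewer placebo events there are and the less likely the curve is to appear. That is the wrong direction for a display filter on safety data.

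At stake is information on timing. The safety and toxicity profile is a secondary objective (SAP 2.2), treatment lasts up to 3 years, and the patients have no macroscopic residual disease. Adverse events are observed from first dose to 28 days after last dose (SAP 7.5.1), so time at risk differs between subjects. The incidence percentages use all as-treated subjects as denominator (SAP 6.2.2), and I found no exposure-adjusted rate in the SAP. For most categories the Kaplan-Meier display is the only planned summary that shows when events begin and allows for unequal follow-up.

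**Working it through.** The threshold is a reporting rule with no derivation, so there is no plan figure to reproduce. The check is how often the rule would let a curve through.

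**Inputs**
- Arm size: SAP 3.1, "Approximately 700 subjects will be randomized in a 1:1 ratio between axitinib vs placebo", so 700 / 2 = 350 per arm. The as-treated number is assumed to be about the same.
- Threshold: 10 per arm, read as each arm. Subjects with a first event are counted; this is an assumption, because the SAP says only events.
- Axitinib rates, for illustration only: Protocol 1.1.4, Table 1, all grades. These come from a second-line metastatic trial with a sorafenib control.
- Placebo rates: in neither document, so assumed over a range.

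**Formulas**
- Threshold as a rate: 10 / 350 = 2.9%.
- One arm reaches 10: T(p) = 1 − Σ(k = 0 to 9) C(350, k) p^k (1 − p)^(350 − k).
- Current rule: P(display) = T(p_axitinib) × T(p_placebo).
- Either-arm rule: P(display) = 1 − [1 − T(p_axitinib)] × [1 − T(p_placebo)].

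**Axitinib arm clearly passing.** At an axitinib rate of 11% or more, T(p_axitinib) is about 1, so the placebo count alone decides.

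| Assumed placebo rate | Expected placebo subjects | P(display), each arm | P(display), either arm |
|---|---|---|---|
| 1% | 3.5 | 0.003 | about 1 |
| 2% | 7.0 | 0.167 | about 1 |
| 3% | 10.5 | 0.606 | about 1 |
| 4% | 14.0 | 0.895 | about 1 |
| 5% | 17.5 | 0.982 | about 1 |

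**By risk ratio R, with placebo rate = axitinib rate / R.** The expected placebo count falls to 10 when R = axitinib rate / (10 / 350).

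| Table 1 term | Axitinib rate | R giving 10 expected on placebo | P(display), R = 3 | R = 5 | R = 10 |
|---|---|---|---|---|---|
| Proteinuria | 11% | 3.85 | 0.83 | 0.25 | 0.006 |
| Hypothyroidism | 19% | 6.65 | 0.999 | 0.86 | 0.13 |
| Palmar-plantar erythrodysesthesia | 27% | 9.45 | 1.00 | 0.99 | 0.47 |
| Fatigue | 39% | 13.65 | 1.00 | 1.00 | 0.88 |
| Hypertension | 40% | 14.0 | 1.00 | 1.00 | 0.90 |

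**Rare in both arms.** At 3% in each arm, the current rule gives 0.606 × 0.606 = 0.367 and the either-arm rule 1 − 0.394 × 0.394 = 0.84. At 3% on axitinib and 1% on placebo, the figures are 0.606 × 0.003 = 0.002 and 0.61.

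**The case against.** A reader might infer that the rule removes the display for the very events most strongly related to axitinib, or that a larger signal is always less likely to be shown. The documents do not support either statement. They give no placebo rates, so they do not show which categories would fail. With the illustrative rates above, hypertension at a risk ratio of 10 would still be shown with probability 0.90. A category at 3% in both arms, with no drug effect, would more often be dropped than shown. Several categories are also broad searches (a whole system organ class, or broad standardised queries), which raises placebo counts. If episodes rather than subjects are counted, the placebo arm reaches 10 more easily and the probabilities above are too low.

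A further defence is that little is lost. The curve is an addition to tables that remain. Other outputs bear on timing:
- SAP 7.5.2: urinalysis and thyroid results at all planned time points, and urine-protein shifts.
- SAP 7.5.4: vital signs and change from baseline.
- SAP 7.4.3: time to dose interruption, reduction and increase.
- SAP 7.3.4: treatment discontinuation over time for events of interest, and room for further exploratory analyses.
- Protocol 9.4.1: individual listings of all adverse events.

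These arguments stand as limits on scope, and they make the point minor. They do not justify the condition. Dose changes and discontinuation are not onset, and listings are not a summary. No other planned summary gives time to onset for palmar-plantar erythrodysesthesia, venous thromboembolism or haemorrhage, for example.

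**Conclusion.** The point holds in a limited form. Read as applying to each arm, the threshold may suppress the onset display for categories below about 3% on placebo, including some strongly drug-related ones. With the axitinib arm clearly passing, the probability of display is about 0.3%, 17% and 61% at assumed placebo rates of 1%, 2% and 3%. It is about 98% at 5%, so categories with a common background, such as hypertension and fatigue, would probably keep their curves. On the illustrative Table 1 rates, proteinuria is the most exposed, followed by thyroid dysfunction and palmar-plantar erythrodysesthesia. For the first two, the laboratory summaries partly fill the gap.

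This rests on about 350 as-treated subjects per arm, on counting subjects, and on assumed placebo rates. Claiming that the events most related to axitinib will be hidden would go beyond the evidence. What can be lost is a figure on timing. Incidence, risk differences, risk ratios and the primary analysis are untouched.

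**What to change.** In SAP 7.5.1.2, change the condition to *at least 10 subjects with the event in either treatment arm*, and show both arms in each figure. Naming subjects also settles whether episodes or first events are counted. In the same edit, reconcile the stated 13 categories with the table, which lists 14 rows (12 if the three cardiovascular rows are merged).

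The cost is one phrase and a few additional figures, some with a nearly flat placebo curve. No new data are needed and no error rate is affected.
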